
General Overview:

This within-subjects study will examine the effects of daily repeated use of cannabis on pain and its relationship to abuse liability. Healthy, non-treatment seeking cannabis smokers (N=16, 8M, 8F) will be admitted to the research center on 5- South of NYSPI for a 16-day inpatient stay. On the first full inpatient day, participants will smoke active cannabis (4.91% CBD/2.98% THC). Days 2-8 will comprise the Inactive Phase, in which placebo cannabis (0% CBD/THC) will be administered 3x/day. The next 7 days (Day 9-15) will be the Active Phase, in which active cannabis (4.91% CBD/2.98% THC) will be administered at the same time points (Table 1). Participants will complete subjective effects visual analog scales and a cannabis rating form daily, and will complete the Cold-Pressor Test and Quantitative Sensory Testing-Thermal Temporal Summation on Days 1, 2, 5, 8, 9, 12, and 15 to explore three critical questions regarding cannabis' therapeutic utility for pain (as illustrated in Figure 1): 1) If abruptly switching active cannabis to inactive cannabis increases experimental pain sensitivity, i.e. hyperalgesia (Day 2-8; red bars) relative to baseline and if these effects parallel measures of cannabis withdrawal such as disrupted mood and sleep; 2) If pharmacological tolerance to the analgesic and abuse-related effects of cannabis is reversed following 7 days of abstinence from active-THC cannabis (by administering 0% CBD/THC, inactive cannabis): defined as a) a significant decrease in CPT latencies and QST-TTS response following active cannabis administration on Day 12 or Day 15 compared to Day 9 (Active Phase), and b) a significant decrease in subjective visual analog scale ratings of abuse, i.e. 'Good Drug Effect' following active cannabis administration on Day 12 or Day 15 (Active Phase) compared to Day 9 (Active Phase); 3) If tolerance is present/develops to repeated, daily smoked cannabis (4.91% CBD/2.98% THC) administration on measures of experimental pain and abuse liability (green bar): defined as a significant increase in CPT latencies and QST-TTS response and 'good drug effect' after active cannabis administration when Day 9 of the Active Phase is compared to Day 1.

Provide the hypothesis for this research.

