Aim 1. Determine the effects of abstinence from active cannabis (by use of 0% THC cannabis) on experimental pain. We hypothesize that (a) abrupt abstinence will result in increased CPT and QST-TTS responses, indicative of withdrawal-induced hyperalgesia.

Aim 2. Determine if a) tolerance is present (Day 1) and is reversed following abstinence from active cannabis (Days 2-8); b) tolerance develops to daily smoked active cannabis (4.91% CBD/2.98% THC; Days 9-15) administration on pain and abuse liability measures. We hypothesize that: (a) existing analgesic tolerance will be reversed following abstinence from active cannabis; (b) over the course of the active cannabis phase, tolerance will develop to cannabis' analgesic but not abuse-related effects.

Include pertinent information about the relationship of the proposed research to previous studies and describe the significance of the proposed research. Be brief.

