- 7) Subjective Effects: A series of 100 mm VAS in which participants indicate how they are feeling at that

moment will be completed 3x/day. The 44-item VAS includes mood, physical symptom, and drug effect descriptors. Based on a cluster analysis, we employed arithmetic means of individual item scores to reduce 34 of the 44 items into eight subscales: good drug effect; miserable; irritable; anxious; bad effect; social; and confused. We also analyze individual VAS drug craving ratings. These subjective measures may detect changes in abuse-related effects as well as changes in mood (miserable, irritable, anxious, cannabis craving) as a function of cannabis condition: 3 min.

8) Objective Sleep Measures: Participants will wear an Actiwatch Activity Monitoring System that tracks gross motor activity (Actiwatch®: Respiromics Company, Bend, OR) and records objective sleep outcomes (hours slept, number of awakenings). We have used this system effectively to demonstrate perturbations in sleep as a function of cannabis withdrawal.

9) Sleep Questionnaire: Participants will complete a sleep questionnaire which consists of a 7-item, 100 mm VAS instrument that assesses the quality of sleep and how many hours slept the previous night and wakefulness in the morning. Participants will be asked to rate symptoms by placing a mark on a line representing a continuum from "not at all" (on the left of the line) to "extremely" (on the right of the line) indicating how the phrase relates to the last night's sleep: 30 sec.

10) Cannabis Rating Form (CRF): Participants rate the strength, liking, desire to take again, good drug effect and bad drug effect of cannabis on a 100mm VAS: 2 min.

Please attach all Questionnaires and Assessments listed above.
No answer provided.

Describe the procedures in sufficient detail so that a reviewer, who is not familiar with them, can comprehend what is to be done and can evaluate any risks.

This study is now in data analysis only, and the following procedures describe the study as it was approved and conducted during the COVID era.

Consent Procedures:

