The effects of smoked cannabis are typically gone within 3 hours. In the rare event that a participant is still impaired at the conclusion of Study Day 15, they will be asked to remain in the laboratory until the effects wear off, and will be paid extra (i.e., \$10 per hour for any additional time they remain in the laboratory). Participants may be sent home in a taxi, for which they will be reimbursed. They will be allowed to leave the facility when they pass the field sobriety test and are medically stable. They will be instructed not to drive a car or use other drugs or alcohol for 8 hours after administration of cannabis; therefore, participants will be required to take public transportation (i.e., bus or subway) from the laboratory on Day 15, for which they will be reimbursed (included in their pay for Day 15).

CPT and QST-TTS

On Days 1, 2, 5, 8, 9, 12, and 15, participants will complete the CPT and QST-TTS pain tasks 30 minutes before the 1000h cannabis administration (baseline), and 0, 15, 30, 45, 60, and 90 minutes post-cannabis administration. Participants will also complete measures of CPT-induced discomfort (CPT-VAS, PIBS) and will continuously rate the magnitude of perceived pain for the temporal heat stimulation of the QST-TTS (Co-VAS) at these time-points. On these days of pain testing, except for Day 15, participants will also complete a cannabis rating form and subjective effects visual analog scales pre-cannabis administration (0945h), for a full-time course after the first cannabis administration (1015h, 1045h, 1115h, 1145h, 1215h), and after each subsequent cannabis administration timepoint (1315h, 1615h). On Day 15, these assessments will conclude with the 1215 time-point. Vital signs will be taken before and after each pain assessment. In addition, vital signs will be taken halfway through the duration of each CPT assessment. If vital sign parameters are exceeded at any point during the CPT task, staff will follow the same assessment procedures as stated in the training section above.

On days when there are no pain assessments, participants will complete just the cannabis rating form and subjective effects battery at 1015h, 1315h, and 1615h.

Cannabis Administration

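### Aim 2(b) predicts no tolerance to abuse-related effects, but under the plan stable ratings can appear only as a non-significant difference test

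*Protocol*

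**What the plan says.** The hypothesis section of the protocol predicts for Aim 2(b) that "over the course of the active cannabis phase, tolerance will develop to cannabis' analgesic but not abuse-related effects". The aim itself asks whether "tolerance develops to daily smoked active cannabis (4.91% CBD/2.98% THC; Days 9-15) administration on pain and abuse liability measures", so development of tolerance is placed in Days 9-15.

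The General Overview sorts the contrasts differently. Under reversal of tolerance it lists "a significant decrease in subjective visual analog scale ratings of abuse, i.e. 'Good Drug Effect' following active cannabis administration on Day 12" or Day 15, each compared with Day 9. Under tolerance that is present or develops, it lists an increase "after active cannabis administration when Day 9 of the Active Phase is compared to Day 1".

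The Statistical/Data Analysis Plan in the protocol and the Statistical Analysis section of the SAP are almost identical. Both specify repeated-measures ANOVA by cannabis condition and day (Days 1-15) and planned comparisons, with F-tests of differences for all comparisons, two-tailed at 0.05. Confidence intervals are named only for describing demographic variables. The protocol says its comparisons are set out below that paragraph, but none follows. The SAP lists none either.

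On status, the protocol says: "This study is now in data analysis only".

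**The concern.** A difference test can support the analgesic half of Aim 2(b): a significant fall in analgesia would be evidence of tolerance. The abuse-related half is different. A significant rise in Good Drug Effect would argue against tolerance, but ratings that simply stay level can only produce a non-significant test. Such a result fits no fall, and it also fits a fall too small for the trial to detect. Which of the two it supports depends on precision, and the plan asks for no measure of precision on any outcome contrast.

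The protocol presents the effect of repeated use on abuse liability as one of the gaps that the study addresses. A statement that abuse-related effects show no tolerance would therefore touch a stated purpose.

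**Working it through.** **Which test bears on the claim.** By its days, the Day 12 or Day 15 versus Day 9 contrast is the one that could show tolerance developing in the active phase. The General Overview files it under reversal, so applying it to Aim 2(b) is a reading, not something the protocol states. The Day 9 versus Day 1 criterion is also a significance criterion. The Day 1-15 factor in the ANOVA is a difference test too, and it mixes active and inactive days. The gap therefore exists under any of these assignments. The figures below are specific to the Day 12/15 versus Day 9 reading.

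**Inputs.** From the sample size justification: effect 0.7 SD, correlation 0.6 (stated typical range 0.60-0.95, for active versus inactive conditions), alpha 0.05, 24 enrolled, 4 dropouts, 20 completers. From the purpose statement and General Overview: N=16. Assumed here: that these correlations also apply to day contrasts, and a smaller fall of 0.35 SD for illustration.

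**The plan's own case.**
- Completers: 24 − 4 = 20.
- SD of a paired difference, in rating SDs: √(2(1−r)) = √0.8 = 0.894 at r = 0.6.
- Standardised difference: 0.7/0.894 = 0.783.
- Noncentral t, two-sided 0.05: power 91.3% at n=20 and 83.3% at n=16.
- A real 0.7 SD fall is therefore missed 8.7% and 16.7% of the time. The documents state no power target to compare with.

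**A smaller fall, one contrast, n=20, 0.35 SD.**
- r = 0.6: 0.35/√0.8 = 0.391, missed 62%.
- r = 0.8: 0.35/√0.4 = 0.553, missed 35%.
- r = 0.9: 0.35/√0.2 = 0.783, missed 9%. This is the same standardised difference as the planning case.
- With n=16 and r = 0.6 the miss is 69%.

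**The either-day rule.** A significant fall on Day 12 or on Day 15 counts. Simulated with the same true fall on both days and equal correlations:

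| True fall | n | r = 0.6 | r = 0.8 | r = 0.9 |
|---|---|---|---|---|
| 0.7 SD | 20 | 2.5% | <0.1% | <0.1% |
| 0.7 SD | 16 | 6.5% | 0.2% | <0.1% |
| 0.35 SD | 20 | 45% | 19% | 2.5% |
| 0.35 SD | 16 | 54% | 28% | 6.5% |

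(Entries are the chance that neither day is significant.)

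**What an interval would show.** The 95% half-width is t × √(2(1−r)/n). At n=20, t = 2.093:
- r = 0.6: 2.093 × √(0.8/20) = 0.42 SD.
- r = 0.8: 2.093 × √(0.4/20) = 0.30 SD.
- r = 0.9: 2.093 × √(0.2/20) = 0.21 SD.

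At r = 0.6, an observed change of exactly zero would leave falls of up to about 0.42 SD compatible with the data. The planned output would not show this.

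**The case against.** The strongest reply is that the hypothesis is a prediction, not a reporting rule. A reader might infer that the investigators intend to report a non-significant test as proof of no tolerance. No text in either document says so, and this point does not claim it. What can be shown is an omission: stable ratings are given no other form of support.

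A second tempting inference is that the study is too small to detect tolerance to abuse-related effects. The documents do not support that. At the only effect size they give, one contrast misses about 9% with 20 completers, and the either-day rule about 2.5%. The large misses need a 0.35 SD fall, which the documents do not supply, and a correlation at the bottom of the stated range.

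Third, the protocol calls this a pilot and says that it explores its questions. That lowers the stakes. However, the analysis sections also call the comparisons a priori tests of each aim's hypothesis, so the exploratory status of this half is not settled.

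Finally, no basis for an equivalence margin appears in the documents, and with the study in data analysis a margin could be post hoc. That objection stands, so a margin is optional in the fix.

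**Conclusion.** The concern holds in a narrow form. One half of one sub-hypothesis predicts no change, and the plan offers only difference tests for it. A stable result would end in p>0.05, which does not establish absence. The analgesic half is unaffected.

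The size is conditional. The concern is minor if only falls near 0.7 SD matter or if the correlation is near 0.9. It is material if smaller falls matter and the correlation is near 0.6, where the either-day rule would miss an assumed 0.35 SD fall about 45% of the time at n=20. These figures rest on the day-based reading of Aim 2(b), on carrying the stated correlations over to day contrasts, and on equal falls on both days. The logical point needs none of these assumptions.

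The disagreement between the General Overview and Aim 2 over which days define development of tolerance is in the text itself. It must be reconciled before the contrast for this half can be named.

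**What to change.** In the SAP:

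1. State which contrast tests development of tolerance over Days 9-15, and make the General Overview and Aim 2 agree.
2. Report the change in Good Drug Effect from Day 9 to Day 12 and from Day 9 to Day 15, each with a 95% confidence interval.
3. Name one instrument. Good Drug Effect is both a subscale of the subjective-effects scales and an item on the Cannabis Rating Form.
4. Name one summary (for example mean, peak or area under the curve) of the post-dose ratings that the three days share. Pain-testing days are rated "for a full-time course after the first cannabis administration (1015h, 1045h, 1115h, 1145h, 1215h", with later ratings on most of them, but "On Day 15, these assessments will conclude with the 1215 time-point". The 1015h-1215h ratings are therefore the common set. Days without pain testing have fewer: "participants will complete just the cannabis rating form and subjective effects battery at 1015h, 1315h, and 1615h". Of these, only the 1015h rating is taken on every one of Days 9-15, so it could show the daily course as support.
5. State that p>0.05 will not be reported as absence of tolerance to abuse-related effects. Describe a stable result by the falls that the interval excludes, and label this half of the hypothesis exploratory.

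Optionally, if a margin can be justified, claim absence only when the interval excludes a larger fall, and label the margin post hoc if data have been seen.

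The cost is SAP wording and two intervals; no new data are needed. The claim becomes harder to make. With no true change, n=20 and correlation 0.6, a 95% interval for Day 15 versus Day 9 would exclude falls beyond assumed margins of 0.35, 0.5 and 0.7 SD in 38%, 66% and 91% of trials.

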All data analyses will be based on models using repeated measures analysis of variance (RM-ANOVA) analyzed as a function of cannabis condition (active vs. inactive) and day (Day 1-15), and sets of planned comparisons, calculated with SPSS or SUPERANOVA statistical packages. The planned comparisons, outlined below, are a priori, and designed to test the specific hypothesis for each aim. Tests of differences for all comparisons will be based on F-statistics with degrees of freedom corrected, depending on the observed within-subject correlation of the measures, using the method of Geiser and Greenhouse or Huynh and Feldt. Results will be considered statistically significant at $p < 0.05$, using 2-tailed tests. Distribution of demographic variables (ethnicity, age, sex) will be described in terms of means, standard deviations, proportions, and 95% confidence intervals, where appropriate.

Please list all references.

1. Nahin, R.L., *Estimates of pain prevalence and severity in adults: United States, 2012*. *J Pain*, 2015. **16**(8): p. 769-80.
2. Dowell, D., T.M. Haegerich, and R. Chou, *CDC guideline for prescribing opioids for chronic pain—United States, 2016*. *Jama*, 2016. **315**(15): p. 1624-1645.
3. LeResche, L., K. Saunders, S. Dublin, S. Thielke, J.O. Merrill, S.M. Shortreed, C. Campbell, and M.R. Von Korff, *Sex and age differences in global pain status among patients using opioids long term for chronic noncancer pain*. *Journal of women's health*, 2015. **24**(8): p. 629-635.
4. Wasserman, R.A., C.M. Brummett, J. Goesling, A. Tsodikov, and A.L. Hassett, *Characteristics of chronic pain patients who take opioids and persistently report high pain intensity*. *Regional anesthesia and pain medicine*, 2014. **39**(1): p. 13.
5. Chou, R., J.A. Turner, E.B. Devine, R.N. Hansen, S.D. Sullivan, I. Blazina, T. Dana, C. Bougatsos, and R.A. Deyo, *The effectiveness and risks of long-term opioid therapy for chronic pain: a systematic review for a National Institutes of Health Pathways to Prevention Workshop*. *Annals of internal medicine*, 2015. **162**(4): p. 276-286.
6. Dunn, K.M., K.W. Saunders, C.M. Rutter, C.J. Banta-Green, J.O. Merrill, M.D. Sullivan, C.M. Weisner, M.J. Silverberg, C.I. Campbell, B.M. Psaty, and M. Von Korff, *Opioid prescriptions for chronic pain and overdose: A cohort study*. *Annals of Internal Medicine*, 2010. **152**(2): p. 85-92.
7. Statistics, N.C.f.H., *Mortality Data for 2017*. 2018.

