Title: Repeated Cannabis Administration on Experimental Pain and Abuse Liability

NCT: 04576507

Document date: April 14, 2025

Statistical Analysis

Overview: All data analyses will be based on models using repeated measures analysis of variance (RM-ANOVA) analyzed as a function of cannabis condition (active vs. inactive) and day (Day 1-15), and sets of planned comparisons, calculated with SPSS or SUPERANOVA statistical packages. The planned comparisons are *a priori*, and designed to test the specific hypothesis for each aim. Tests of differences for all comparisons will be based on F-statistics with degrees of freedom corrected, depending on the observed within-subject correlation of the measures, using the method of Geiser and Greenhouse or Huynh and Feldt. Results will be considered statistically significant at $p < 0.05$, using 2-tailed tests. Distribution of demographic variables (ethnicity, age, sex) will be described in terms of means, standard deviations, proportions, and 95% confidence intervals, where appropriate.

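### Aim 2(b) predicts tolerance in analgesia but not in abuse-related effects, yet no planned test compares the two outcomes and no rule says how the negative half will be concluded

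*Protocol*

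**What the plan says.** The hypothesis section of the Protocol, Aim 2(b), states that over the active phase "tolerance will develop to cannabis' analgesic but not abuse-related effects".

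The General Overview gives the only criteria that compare late active-phase days with Day 9. For pain the criterion is "a significant decrease in CPT latencies and QST-TTS response following active cannabis administration on Day 12 or Day 15 compared to Day 9". For abuse liability it is, separately, "a significant decrease in subjective visual analog scale ratings of abuse, i.e. 'Good Drug Effect' following active cannabis administration" on the same days. The General Overview files both under its question 2, reversal of tolerance. Its question 3, on tolerance being present or developing, is defined by Day 9 against Day 1.

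The Protocol's Statistical/Data Analysis Plan uses RM-ANOVA, "analyzed as a function of cannabis condition (active vs. inactive) and day (Day 1-15), and sets of planned comparisons", at two-sided 0.05. It then says "The planned comparisons, outlined below, are a priori", but no list follows. The SAP repeats the paragraph and describes the comparisons as "designed to test the specific hypothesis for each aim", again without listing them. Neither document has an outcome-by-day term, a contrast between pain and Good Drug Effect, or a margin for concluding that an effect did not diminish.

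**The concern.** Each stated test has the null that its own outcome does not change. The null that bears on Aim 2(b) is that both outcomes lose the same standardised amount, and no planned test addresses it. A significant result next to a non-significant one does not show that the two changes differ. With equal, moderate losses, chance will often put them on opposite sides of 0.05.

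This matters because a loss of pain relief with the abuse-related effect preserved is the study's most distinctive possible finding. It goes directly to the stated purpose of relating pain effects to abuse liability.

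**Working it through.** **Inputs from the documents.** The sample-size justification gives α = 0.05, d = 0.7, r = 0.6 and n = 20 completers (24 less 4 dropouts). Two-sided testing is in the analysis plan. N = 16 stands in Study Details and the General Overview.

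**Inputs assumed.** The true loss is equal in both outcomes at 0.3, 0.4, 0.5 or 0.7 of a single-day SD. The correlation between the outcomes' changes is 0 to 0.5. Every outcome is signed so that a positive change is a loss of effect. The documents give none of these.

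**The plan's own figure.** The SD of a change is √(2(1−0.6)) = 0.894, so d = 0.7 gives dz = 0.7/0.894 = 0.783. A two-sided paired t-test at n = 20 then has 91.3% power, and 20 is the smallest n that reaches 90%. No power target is stated. If 0.7 is read as dz, power at n = 20 is 84.3%. The stated 20 is reproducible either way.

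**False dissociation under equal loss.** Let p be the power of one Day 15 v Day 9 test. With independent changes:
- one pain test: p(1−p)
- CPT and QST-TTS both required: p²(1−p)
- either pain test suffices: [1−(1−p)²](1−p)

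At 0.4 SD, p = 0.476. The three rates are 0.476×0.524 = 25%, 0.227×0.524 = 12% and 0.725×0.524 = 38%.

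Simulation (40,000 trials per cell, n = 20) extends this to correlations of 0.3 and 0.5. Each range runs over correlations 0 to 0.5:

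| Equal loss | p | One pain test | Both required | Either suffices |
|---|---|---|---|---|
| 0.3 SD | 30% | 15-21% | 6% | 24-35% |
| 0.4 SD | 48% | 17-25% | 9-12% | 26-38% |
| 0.5 SD | 66% | 15-22% | 9-15% | 22-30% |
| 0.7 SD | 91% | 6-8% | 5-7% | 8-9% |

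At n = 16 with one pain test, the rate is 13-25% over 0.3-0.5 SD and 10-14% at 0.7 SD. If 0.7 is read as dz, n = 20 gives 13% with independent changes and 9-11% at correlations 0.6 to 0.3.

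**The either-day rule as written** (n = 20, one pain measure). If the full loss is present by Day 12, the rate is 10-25% at 0.3-0.5 SD and 2-3% at 0.7 SD (correlations 0-0.6). If half the loss is present by Day 12, it is 15-24% and 6-7% (correlations 0-0.5).

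**Direct contrast.** The within-person difference between the two standardised changes has mean zero under equal loss. A two-sided 5% test is therefore significant in the predicted direction in 2.5% of trials (2.4-2.6% in simulation). This holds because the losses are equal on the scale being tested.

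**What the contrast does not show.** With true losses of 1.0 SD (pain) and 0.5 SD (abuse) at n = 20, it is significant in 39-66% of trials. In 17-38% of all trials it is significant while Good Drug Effect has itself fallen significantly.

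**The case against.** Three objections carry weight.

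1. **The decision rule is inferred.** No section says that a significant and non-significant pair will be reported as a dissociation, and the relevant criteria are labelled as reversal. This stands. A reader might infer that the plan commits to the two-test reading, but the documents support only that nothing else is offered.

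2. **The size depends on the assumed loss and on the pain criterion.** A reader might take 15-25% as the general error rate. The documents do not support that. At their only effect size, a raw d of 0.7 with n = 20, it is 6-8%, and if both pain measures must fall, 15% is about the ceiling. Nor would the opposite pattern (abuse but not pain) always be equally common: with both pain tests required it appears in about 20-37% of trials at 0.3-0.5 SD. In reply, the sample-size text does not tie 0.7 to any outcome and discusses active against inactive cannabis. If 0.7 is that drug effect, partial tolerance of 43-71% (0.3/0.7 to 0.5/0.7) gives 0.3-0.5 SD. That too is a reading, not a stated fact.

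3. **A contrast answers a narrower question than the hypothesis.** A larger loss in pain than in Good Drug Effect does not mean no loss in the latter. This stands and shapes the fix.

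The study also calls itself a pilot meant to explore its questions. That lowers the stakes but does not supply a test for the stated hypothesis.

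**Conclusion.** The gap is real. Aim 2(b) asserts a difference between outcomes, and neither document plans a test of that difference or a rule for its negative half.

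The size is conditional. Under equal loss in SD units, n = 20, r = 0.6, one Day 15 v Day 9 test per outcome and between-outcome correlation 0-0.5, the misleading pattern appears in about 15-25% of trials for losses of 0.3-0.5 SD and 6-8% at 0.7 SD. It is about 5-15% over 0.3-0.7 SD if CPT and QST-TTS must both fall. If either suffices, it is about 22-38% at 0.3-0.5 SD and 8-9% at 0.7 SD. The comparable figure for a direct contrast is 2.5%.

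This is a cheap improvement to the plan and does not invalidate it.

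**What to change.** Add one planned contrast for Aim 2(b) to the SAP. The Protocol says the study is in data analysis only, so label it with the date it was added.

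- For each participant, take the Day 9 to Day 15 change in CPT tolerance latency and in Good Drug Effect, over the same window after the 1000h dose. Sign both so that positive means loss, and divide each by its Day 9 SD.
- Test the within-person difference and report its 95% CI. Repeat with each change as a proportion of the Day 9 effect.
- Treat a significant contrast as necessary but not sufficient. Alone it supports only greater analgesic than abuse-related tolerance. To claim no abuse-related tolerance, also require the CI for the Good Drug Effect change to exclude a loss fixed in advance as meaningful.
- Otherwise report both changes with CIs and claim no dissociation.

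**Cost.** The data are already collected. The result depends on the standardisation, hence the proportional repeat. Power falls. With no abuse loss, n = 20 and correlation 0.3, the contrast has 52% against 64% for the two-test pattern at a 0.5 SD pain loss, and 80% against 89% at 0.7 SD. The CI condition lowers it further: the expected half-width is about 2.093×0.894/√20 = 0.42 SD, so a smaller margin will seldom be excluded.
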